### **5.3.3 Sensitivity Analyses for Primary Endpoint**

Sensitivity analyses of the primary endpoint will be conducted in order to detect a potential bias with regard to the primary analysis.

- The analysis on primary endpoint will be replicated on Safety evaluable population to assess the response rate of all patients enrolled and treated in this study.
- The intracranial ORR will include patients with unconfirmed complete response (CR) or partial response (PR) based on the safety population. Unconfirmed Intracranial ORR will be analyzed using the same methods as described in Section 5.3.2.

In addition, a summary of concordance between investigator and IRC intracranial response assessments, according to RECIST v1.1 with a modified measurability definition for intracranial lesions ( $\geq 0.5$  cm by MRI) and allowing up to five intracranial target lesions, will be provided.

### **5.3.4 Supplementary Analyses for Primary Endpoint**

Not applicable.

#### **5.3.4.1 Subgroup Analyses for Primary Endpoint**

The consistency of the primary efficacy results will be examined in subgroups defined by demographic characteristics and clinical and biological prognostic factors. Summaries of intracranial ORR, including 95% Pearson-Clopper CIs, will be produced for each of the defined subgroups, and displayed in a Forest plot ([Lewis and Clarke 2001](#)).

The subgroups to be considered include, but may not be limited to, the following:

- Age ( $\leq 65$  years,  $>65$  years)
- Race (non-White, White)
- Sex (female, male)
- Eastern Cooperative Oncology Group (ECOG) performance status (0, 1)
- programmed death ligand 1 (PD-L1) status
- Lactic Acid Dehydrogenase (LDH) ( $\leq$  upper limit of normal [ULN],  $>ULN$ )

- BRAF mutation subtype (V600E, V600K)
- Extracranial sum of longest diameter
- Number of target lesion (intracranial, extracranial)
- Receiving prior steroid therapy
- Organ involvement (site of target lesion): patients with brain lesion(s) only, patients with brain lesion(s) and other lesions.

## **5.4 SECONDARY ENDPOINTS ANALYSES**

Unless otherwise noted, all efficacy analyses will be performed on both the evaluable patient population and all treated patients (safety population).

### **5.4.1 Key/Confirmatory Secondary Endpoint**

Not applicable.

### **5.4.2 Supportive Secondary Endpoints**

#### **5.4.2.1 Intracranial Objective Response Rate – RECIST**

Intracranial ORR is defined as the proportion of patients with either a CR or PR in their intracranial disease based on two consecutive assessments  $\geq 4$  weeks apart, as determined by the investigator according to RECIST v1.1 with a modified measurability definition for intracranial lesions ( $\geq 0.5$  cm by MRI) and allowing up to five intracranial target lesions.

The intracranial ORR will be presented together with a 95% Pearson-Clopper CI.

#### **5.4.2.2 Extracranial Objective Response Rate – RECIST**

Extracranial ORR is defined as the proportion of patients with either a CR or PR in their extracranial disease based on two consecutive assessments  $\geq 4$  weeks apart, as determined by the investigator according to RECIST v1.1.

The extracranial ORR will be presented together with a 95% Pearson-Clopper CI.

#### **5.4.2.3 Overall Objective Response Rate – RECIST**

Overall ORR is defined as the proportion of patients with either a CR or PR in their overall disease (i.e., including intracranial and extracranial disease) based on two consecutive assessments  $\geq 4$  weeks apart, as determined by the investigator according to RECIST v1.1.

The overall ORR will be presented together with a 95% Pearson-Clopper CI.

#### **5.4.2.4 Intracranial, Extracranial and Overall Progression-Free Survival – RECIST**

Intracranial, extracranial, and overall progression-free survival (PFS) are defined as the time from study treatment initiation to the first occurrence of disease progression, as

determined by the investigator according to RECIST v1.1, or death from any cause, whichever occurs first. Data for patients who have not experienced disease progression or death at the time of analysis data cutoff will be censored at the last evaluable tumor assessment date.

Kaplan-Meier methodology will be used to estimate median intracranial, extracranial, and overall PFS. Kaplan-Meier curves will be provided. The 95% CI of the median PFS will be constructed using the Brookmeyer and Crowley method (Brookmeyer and Crowley 1982).

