Study treatment may be continued beyond progression per RECIST v1.1 if pseudoprogression due to the effects of immunotherapy is suspected to have occurred or if disease progression is limited to ≤ 3 intracranial lesions that can be controlled with SRT. Clinically stable patients who have a favourable benefit-risk ratio may continue study treatment beyond progression per RECIST v1.1 if all of the following criteria are met:

- Clinically stable patient with evidence of clinical benefit and favourable benefit-risk ratio as determined by the investigator
- Absence of symptoms and signs (including laboratory values, such as new or worsening hypercalcemia) indicating unequivocal disease progression
- No decline in Eastern Cooperative Oncology Group (ECOG) Performance Status that can be attributed to disease progression
- Absence of tumour progression at critical anatomical sites (e.g., leptomeningeal disease) that cannot be managed by protocol-allowed medical interventions
- Documented investigator/patient discussion of treatment options alternative to continuing study treatment at the time of RECIST v1.1-defined disease progression
- *Consultation with the Medical Monitor is advised*

Study treatment will be discontinued in patients who continue treatment beyond disease progression per RECIST v1.1 if clinical deterioration because of disease progression occurs at any time subsequently or if persistent disease growth is confirmed on follow-up disease assessments performed approximately four weeks later. Post-progression assessments may be conducted sooner if necessary e.g., due to clinical progression. The disease status of patients who continued study treatment and underwent intracranial SRT will be determined by the investigator according to RECIST v1.1 modified by excluding any treated lesions from the sum of largest diameters from baseline onwards.

Patients will attend a Study Treatment Discontinuation Visit after 28 ± 7 days of their last study treatment dose. All adverse events will be reported until 30 days after the last study treatment dose. After the Study Treatment Discontinuation Visit, patients who have

not yet progressed will be followed every 8 or 12 weeks for disease status until disease progression is confirmed, and all patients will be followed every three months for survival and new anti-cancer treatments.

[Figure 2](#) presents an overview of the study design.

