3.3.5 Rationale for Treatment beyond Disease Progression per RECIST v1.1

Patients in either study cohort may continue treatment beyond disease progression per RECIST v1.1 for two reasons: possible pseudoprogression due to immunotherapy, or disease progression is limited to ≤ 3 intracranial lesions that may be controlled by SRT.

In studies of immunotherapeutic agents, complete response (CR), PR and stable disease (SD) have each been shown to occur after radiographic evidence of an apparent increase in tumour burden. This initial increase in tumour burden caused by immune-cell infiltration in the setting of a T cell response has been termed pseudoprogression ([Hales et al. 2010](#)). In single agent atezolizumab studies (Study PCD4989g – see Atezolizumab Investigator's Brochure), evidence of tumour growth followed by a response was observed in several tumour types. In addition, in some responding patients with radiographic evidence of progression, biopsies of new lesions or areas of new growth in existing lesions revealed infiltrating immune cells and no viable cancer cells. Because of the potential for a response after pseudoprogression, this study will allow treatment in either cohort to continue after apparent radiographic progression per RECIST v1.1, provided the benefit-risk ratio is judged to be favourable (see criteria in Section [3.1](#)).

The blood brain barrier limits drug delivery to intracranial disease sites ([Agarwala et al. 2000](#)). A probable result of this sequestration is that, while disease outcomes have improved with the introduction of new systemic agents (see Section [1.1](#)), intracranial disease progression despite stable or responding extracranial disease has become more common ([Soliman et al. 2015](#)). Though randomized studies evaluating systemic treatment with SRT are limited, the practice of managing brain lesions with SRT in patients whose extracranial disease is controlled by systemic treatment has become a common clinical practice. The value of this approach has been supported by multiple retrospective analyses in melanoma patients receiving SRT with immunotherapy and/or targeted agents ([Anderson et al. 2017](#); [Choong et al. 2017](#), [Ahmed et al. 2016](#); [Mathew et al. 2013](#); [Knisely et al. 2012](#)).

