4.5.6 Tumour and Response Evaluations

All measurable and non-measurable lesions must be documented at screening (within 28 days prior to initiation of study treatment). Previously irradiated lesions should not be

Cobimetinib, atezolizumab, vemurafenib — F. Hoffmann-La Roche Ltd

74 / Protocol MO39136, Version 5.0

selected as measurable (target) lesions. Tumour assessments performed as standard of care prior to obtaining informed consent and within 28 days prior to initiation of study treatment do not have to be repeated at screening. All measurable and evaluable lesions should be re-assessed at each subsequent tumour evaluation. Intracranial and extracranial tumour assessments after end of Cycle 2 should be conducted every 8 weeks \pm 1 week regardless of study treatment delays through 24 months and then every 12 weeks \pm 1 week thereafter until confirmed disease progression per RECIST v1.1, initiation of a new anti-cancer treatment, withdrawal of consent, study termination by the Sponsor or death, whichever occurs first.

Tumour assessments must be performed independently of changes to the study treatment administration schedule (i.e. when treatment is withheld). If a tumour assessment has to be performed early or late, subsequent assessments should be conducted according to the original schedule based on the date of first study treatment administration.

Tumour assessments are to continue according to schedule in patients who discontinue treatment for reasons other than disease progression (unless subsequent anti-cancer therapy is initiated).

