Intracranial disease must be followed by MRI. Extracranial tumour assessments will include contrast-enhanced CT or MRI scans of the chest, abdomen and pelvis. Imaging of the neck should be included if clinically indicated. If a CT scan with contrast is contraindicated (e.g., in patients with impaired renal clearance), a non-contrast CT scan of the chest may be performed along with MRI scans of the abdomen, pelvis and head. In the event a positron emission tomography (PET)/CT scanner is used for tumour assessments, the CT portion of the PET/CT must meet criteria for diagnostic quality. Clinical disease assessments by physical examination should be performed for patients with palpable/superficial lesions. Tumour measurements for each patient should be made by the same investigator or radiologist, if feasible, ideally using the same assessment technique or procedure throughout the study. Results must be reviewed by the investigator before dosing at the next cycle.

Disease status will be determined according to RECIST v1.1 (see [Appendix 5](#)) with a modified measurability definition for intracranial lesions (≥ 0.5 cm by MRI) and allowing up to five intracranial target lesions (in addition to any extracranial target lesions). Exploratory analyses of disease status will include evaluations by immune-modified RECIST (see [Appendix 6](#)), RECIST v1.1 modified by excluding any SRT lesions from the sum of largest diameters from baseline onwards (if applicable), and iRANO criteria (see [Appendix 7](#)).

Disease responses for all endpoints will be confirmed by two consecutive assessments at least four weeks apart. Tumour assessments showing disease progression must be repeated approximately four weeks later regardless of whether treatment is continued

beyond progression. If disease progression is not confirmed, the subsequent tumour assessment should occur at least four weeks later. However, post-progression assessments may be conducted sooner for patients continuing study treatment beyond progression if necessary e.g., due to clinical progression. Objective response (CR or PR) must be confirmed by repeat assessments ≥ 4 weeks after initial documentation. In the case of SD, tumour measurements must meet criteria for SD ≥ 6 weeks after initiation of study treatment.

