#### **5.4.2.5 Intracranial, Extracranial and Overall Duration of Response – RECIST**

For patients who achieve respectively an intracranial, extracranial, and objective response, intracranial, extracranial, and overall DOR are defined as the time from the first occurrence of a documented objective response based on two consecutive assessments  $\geq 4$  weeks apart to disease progression or death from any cause (whichever occurs first), as determined by the investigator according to RECIST v1.1. The censoring method for DOR is the same as the one described for PFS analysis in Section 5.4.2.4.

The Kaplan-Meier approach will be used to estimate median DOR. The 95% CI of the median DOR will be estimated using the Brookmeyer and Crowley method.

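### Imaging of both sites normally stops at progression in either, yet site-specific PFS and DOR count any later death and censor survivors at the last scan, so censoring depends on outcome and the direction of bias depends on follow-up

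*SAP*

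**What the plan says.** **Imaging.** Protocol 4.5.6 schedules intracranial and extracranial assessments together, every 8 weeks to 24 months and then every 12 weeks "thereafter until confirmed disease progression per RECIST v1.1, initiation of a new anti-cancer treatment, withdrawal of consent, study termination by the Sponsor or death", whichever comes first. A scan showing progression "must be repeated approximately four weeks later regardless of whether treatment is continued". Note w to the Cohort 2 schedule (Appendix 2) repeats the rule; note s for Cohort 1 (Appendix 1) leaves out new treatment. Nothing tells sites to go on imaging a site that has not progressed. Protocol 3.1 continues survival follow-up every three months for everyone.

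**Analysis.** SAP 5.4.2.4 defines the three PFS endpoints in one sentence, with all-cause death as an event however long after the last scan. Only patients with neither event are censored, and they "will be censored at the last evaluable tumor assessment date". For DOR, SAP 5.4.2.5 says: "The censoring method for DOR is the same as the one described for PFS analysis". SAP 5.5.1.8 applies the same methods to IRC intracranial PFS and DoR. The one limit on deaths in efficacy analyses is a complete death date (SAP 5.1). No rule covers progression in the other site, missed scans or new therapy, and the definition does not say that progression must lie in the named site.

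**The concern.** Once one site progresses, the other usually goes unobserved for progression but remains observed for death. Whether a patient then stays in the risk set for the unobserved site depends on whether that patient later dies. Kaplan-Meier estimation needs censoring that carries no information about the outcome, and this rule breaks that requirement. Progression in the unscanned site during the gap is never seen, so a late death stands in for it. Intracranial and extracranial PFS and DOR are secondary endpoints of a trial about CNS disease. The curves would mix site control with survival after progression, and could shift between the primary and final analyses because of the rule rather than the treatment.

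**Working it through.** The plan gives no PFS or DOR figure, so there is none to reproduce.

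**1. One patient followed through the rules.** Extracranial progression is seen at month 4. The confirmation scan about four weeks later makes the last brain MRI about month 5.
- Dies at month 14: intracranial PFS is an event at month 14, with 14 − 5 = 9 months unimaged.
- Alive at cutoff: censored at about month 5.

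**2. Two opposing forces.** The estimator is S(t) = ∏(1 − d/n) over event times.
- Unseen progression between months 5 and 14 is moved to the death date. Early d is too small and the curve too high.
- Survivors leave n at month 5, while patients who will die before cutoff stay in n and later enter d. Late d/n is too large and the curve too low.

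Longer follow-up leaves fewer survivors, so the second force fades and the first grows.

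**3. Size, by simulation.**
- From the documents: 8-week scans, both sites stopping at a 4-week confirmation scan, cutoffs 6 and 24 months after the last patient is enrolled (SAP 5.1).
- Assumed, not in the documents: exponential times; 18-month uniform accrual; death before progression with median 40 months; shared gamma frailty variance 0, 0.5 or 1; progression hazard in a site unchanged by progression elsewhere. Medians in months (intracranial progression, extracranial progression, survival after first progression): 6/6/6, 6/9/9, 6/15/9, 8/12/12, 6/9/15, 10/10/24, 6/9/4.
- Results per cutoff: 7 median sets × 3 frailty values × 2 sites = 42, with 150,000 patients per scenario.
- Bias = 100 × (S under the SAP rule − S with that site scanned until its own progression or death).

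| Cutoff | 6-month rate | 12-month rate | 18-month rate | Median (months) |
|---|---|---|---|---|
| Primary | −0.7 to +1.6 | −3.8 to +1.2 (up in 24 of 42) | −7.5 to −0.2 (down in 42 of 42) | −1.0 to +0.5 |
| Final | +0.5 to +2.7 | +1.8 to +5.1 (up in 42 of 42) | +1.1 to +4.9 (up in 42 of 42) | 0 to +1.6 |

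Deaths more than 16 weeks (two scan intervals) after the last scan were 3.0–11.9% of patients at the primary cutoff and 8.5–31.8% at the final one. Patients alive and censored after progression in the other site were 5.0–26.9% and 0.6–18.5%.

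**4. One scenario in full.** Extracranial PFS, medians 6/9/15, frailty variance 1:
- Primary: 12 months, 40.4% becomes 41.5% (+1.1); 18 months, 27.6% becomes 26.1% (−1.5).
- Final: 12 months, 41.0% becomes 45.8% (+4.8); 18 months, 28.5% becomes 32.9% (+4.4); median 9.2 becomes 10.6 months (+1.4).

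**5. Sensitivity.**
- If 30% of patients keep being scanned beyond progression (assumption), the final 12-month bias is +1.1 to +3.5 and the primary 18-month bias −4.8 to −0.1.
- Five scenarios with 24-month accrual, frailty variance 0.5 and post-progression medians of 6–10 months gave, at 12 months, +0.4 to +1.5 (primary) and +2.8 to +3.9 (final), and −2.6 to +0.1 at 18 months (primary).
- A further run gave about +3 to +6 at 12 months (final), and 0 to +2 at 12 months and −3 to +0.5 at 18 months (primary).

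**The case against.** **The stop is not universal.** Patients with suspected pseudoprogression, or with progression limited to three or fewer "intracranial lesions that can be controlled with SRT", may continue treatment, and Protocol 3.1 adds: "The disease status of patients who continued study treatment and underwent intracranial SRT will be determined by the investigator". Radiotherapy-assisted PFS (SAP 5.5.1.5) needs those scans. This stands. It shrinks the problem, as the 30% run shows, without removing it.

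**The site is not named.** Protocol 4.5.6 says progression per RECIST v1.1 without saying where. Reading it as any site is an inference, though Table 1 of Appendix 5 makes progression in any target or non-target lesion, or a new lesion, overall progression.

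**Protocol 3.3.5 gives no rate.** A reader might infer from it that brain-first failure will be common here. It says only that "intracranial disease progression despite stable or responding extracranial disease has become more common", with no figure for this trial, and it says so to justify continued treatment, under which some of these patients stay assessed.

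**Precision is low and the analysis descriptive.** With 50 patients, the plan's own interval for a 40% response rate is 26.4% to 53.6%, or 13.6 points either side. A shift of 2 to 6 points is well inside that. This limits the consequence, but a systematic error is not reported by a confidence interval.

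**Replacement rules are not neutral.** In the five scenarios above, counting a death only within two scan intervals, and otherwise censoring at the last scan, cut the final 12-month bias to +1.3 to +1.7. It left 18-month bias of +2.3 to +4.7 at both cutoffs, against −2.6 to +0.1 (primary) and +2.2 to +2.8 (final) under the SAP rule. Protocol 6.4.2 also defines PFS and DOR with all-cause death. Both points argue against replacing the main analysis.

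**Conclusion.** The structural defect follows from the text alone: a shared scan stop, continuing survival follow-up, unlimited deaths as events, and survivors censored at the last scan. Site-specific PFS and DOR, and their IRC intracranial versions, have outcome-dependent censoring and unseen progression.

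A reader might infer that the site-specific curves are simply biased upward. The documents do not support that. The censoring of survivors pulls late estimates down, and at the primary cutoff the 18-month rate was too low in all 42 results of the main run. Upward bias, about 2 to 6 points at 12 months, is a feature of the final analysis only, and every size here rests on assumed hazards and correlation between sites. DOR shares the rule but was not quantified. Overall PFS, OS and the primary intracranial ORR are not affected by the other-site mechanism.

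**What to change.** In SAP 5.4.2.4, 5.4.2.5 and 5.5.1.8:

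1. State that progression must be in the named site.
2. Keep the protocol-defined Kaplan-Meier estimates, and beside them show the Aalen-Johansen cumulative incidence of first failure by site: intracranial only, extracranial only, both, and death without progression. It needs no imaging after the first site fails. For 5.5.1.8, say whose extracranial assessment is used, since that section covers intracranial disease only.
3. Report how many patients lost imaging of a site because the other site progressed, and how many because new therapy began. The second count matters because first-failure incidence does not by itself resolve scans stopped by new therapy before any progression.
4. As a sensitivity analysis only, count a death as the site event when it falls within two scheduled scan intervals of that site's last scan, and otherwise censor at that scan. Note that this censoring is itself informative if the sites are correlated.
5. Record the additions in SAP Appendix 1.

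The cost is SAP wording, one extra table and one figure, with no new data. First-failure incidence answers a somewhat different question from site-specific PFS and does not yield a site-specific DOR, so it supplements the planned curves and does not replace them.

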#### **5.4.2.5 Intracranial, Extracranial and Overall Duration of Response – RECIST**

For patients who achieve respectively an intracranial, extracranial, and objective response, intracranial, extracranial, and overall DOR are defined as the time from the first occurrence of a documented objective response based on two consecutive assessments  $\geq 4$  weeks apart to disease progression or death from any cause (whichever occurs first), as determined by the investigator according to RECIST v1.1. The censoring method for DOR is the same as the one described for PFS analysis in Section 5.4.2.4.

The Kaplan-Meier approach will be used to estimate median DOR. The 95% CI of the median DOR will be estimated using the Brookmeyer and Crowley method.

